Randomization. Our biostatistician will oversee the process of randomization of subjects to either the NO-ASPIRATE or usual care group. He will develop a blocked randomization procedure, using different sized blocks, to ensure balanced assignment without being able to predict group assignment.¹⁶⁶ Because many subjects will be intubated with the specialized SS-ETT (about 65% from historical data), we will stratify randomization by type of ETT to ensure that approximately half of those with and without the SS-ETT are randomly assigned to each group. Stratification will help to address type of tube as a potential confounding variable, and will allow for secondary sub-group analysis. A member of the study team not involved in data collection will place group assignments for each type of ETT in numbered, sealed, opaque envelopes. Upon enrollment, study personnel will identify the type of ETT, and open the appropriate envelope to determine group assignment. Only study team members who provide the intervention will know the subjects' assigned groups. ICU personnel, as well as subjects and family members, will be blinded to the assignment.

Intervention. Following enrollment, the RA will collect baseline data, implement the assigned intervention (NO-ASPIRATE or usual care/sham), and collect specimens. The RA will then implement the intervention as designated by study arm every 4 hours. *Figure 4 summarizes the procedures for each group.*

To control for possible differences in usual oral care practices, the RA will perform oral cleansing and suctioning with a suction swab after delivering the NO-ASPIRATE or sham intervention using the hygiene components from the oral care kit. The RA will also perform tooth brushing every 12 hours. Oral antisepsis will be done after obtaining specimens for α -amylase. Some subjects may require additional oral suctioning for secretion management; staff will use the available tonsil suction device for oral suctioning in-between the scheduled interventions and document in the medical record. Additional necessary oral suctioning will be recorded and controlled for, if applicable.

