Paired specimens of oral and tracheal aspirates for α -amylase. The RA will obtain an oral specimen for α -amylase at enrollment and every 12 hours (concurrently with a tracheal aspirate) to compute the tracheal/oral ratio. Oral secretions will be collected into a trap during the NO-ASPIRATE or usual care/sham intervention. Following this procedure, a tracheal aspirate will be obtained for detection of α -amylase. Although Weiss detected α -amylase in BAL specimens up to 72 hours post intubation, others have suggested more frequent collection.^{46,97} Obtaining specimens every 12 hours will provide longitudinal data regarding microaspiration, and facilitate identification of clinical factors that contribute to its occurrence. The RA will suction the subject's ETT per standard procedure (closed ETT suction with hyperoxygenation via the ventilator before the procedure) to retrieve tracheal secretions into a specimen trap. We tested these procedures in a preliminary study.⁹³ Since ETT suctioning should be done based on identified need,¹²¹ the RA will assess the subject for cues identifying suctioning need before obtaining the specimen: audible crackles over the trachea, sawtooth

pattern on the ventilator flow waveform, cough, high peak inspiratory pressure, visible secretions, or changes in oxygen saturation.^{85,122} *If suctioning is not indicated at the scheduled time, the RA will collaborate with the subject's nurse to notify the RA if suctioning is clinically indicated within a 2-hour period to ensure complete collection of samples. Time of specimen collection (or omissions) will be noted. The usual care oral antisepsis done for all subjects will be done AFTER specimen collection to prevent contamination.* All oral and tracheal specimens will be frozen to -20° C until the assays are run. A compact medical lab freezer, used solely for purposes of this study, will be purchased and located on or near one of the study units for easy storage. Specimens will be regularly transported on ice to the APH Specialty Diagnostic Laboratory.

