The NO-ASPIRATE or usual care/sham intervention will be administered by a member of the research team every 4 hours. The decision for this interval was based on the volume of oral secretions measured in our preliminary studies,²⁵ and non-experimental quality improvement studies that implemented oropharyngeal suctioning at 4- and 6-hour intervals.^{64,94} Concurrently with delivery of the interventions, paired specimens of oral and tracheal secretions will be obtained at baseline and every 12 hours for assays of α -amylase. Tracheal specimens will be obtained based on the subject's need for ETT suctioning.

List any collaborating sites where human subjects research will be performed, and describe the role of those sites and collaborating investigators in performing the proposed research. Explain how data from the site(s) will be obtained, managed, and protected.

Subjects will be patients in one of the ICUs at Orlando Regional Medical Center. The study team has extensive experience conducting clinical studies in these units. Three of our co-investigators are employees at the site. [name] is chairman of the corporate Critical Care Committee, which will facilitate communication across units. As Director for the Center for Nursing Research, [name] helps to establish collaborations between the university and hospital. [name] oversees the APH Specialty Diagnostic Laboratory where the α -amylase assays will be run. Additionally, [name] has an appointment as a Nurse Scientist at the agency, which also facilitates collaboration and the ability to conduct research in the setting.

Data will be recorded in electronic means on password-protected computers. The subject's medical record number will be used to retrieve study-related data from the electronic medical record (EMR). All subjects will be issued a unique code that will be recorded in the research files. All data will be de-identified for final analysis and findings will be reported in aggregate. A key, pairing the medical record number and unique identification code, will be kept separate from all data in a locked file in [name] research office at UCF. Access to this information will be limited and only on a "need-to-know" basis.

B. SOURCES OF MATERIALS

Describe the research material obtained from living individuals in the form of specimens, records, or data.

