The research materials for this study include data from the subject's medical record and observation. Oral secretion and sputum specimens (endotracheal aspirate) for assays of α -amylase will be obtained at baseline and every 12 hours for up to 14 days. Specimens will be discarded after analysis. Demographic and physiological data will be obtained daily from the EMR. Data to determine presence of VAC will be obtained daily and for 2 days after the last intervention has been delivered. VAC-related data will be obtained from the EMR.

Describe any data that will be collected from human subjects for the project described in the application.

At baseline (enrollment), we will collect demographic, physiological, and ventilator data (Table 1). Data include age, gender, ethnicity, race, diagnosis, ETT information (type of tube and time of intubation), and severity of illness data. Physiological data will be obtained from the medical record at time of enrollment and per schedule (either daily or every 4 hours): temperature, vital signs, and sedation score. Information related to types of enteral tubes and nutritional support will be collected. Ventilator data will include mode of ventilation, set respiratory rate, positive end expiratory pressure, pressure support, and fraction of inspired oxygen. Ventilator data will assist in determining VAC. Temperature and results of tracheal aspirate cultures will be obtained from

the EMR for secondary analysis of infection or non-infection related VAC. Upon completion of the study, additional outcome data will include ICU length of stay, duration of mechanical ventilation and cost data from the hospital database for comparison of groups.

Indicate who will have access to individually identifiable private information about human subjects.

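### The enrolment α-amylase pair, called baseline, is taken during and after the first assigned procedure, so the trial has no pre-treatment amylase value

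*Combined protocol and SAP*

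**What the plan says.** Under Procedures, the Randomization section has study personnel open the envelope at enrolment. The Intervention section then gives the sequence: "Following enrollment, the RA will collect baseline data, implement the assigned intervention (NO-ASPIRATE or usual care/sham), and collect specimens".

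The section on paired specimens fixes when each half of the pair is taken. For the oral half: "Oral secretions will be collected into a trap during the NO-ASPIRATE or usual care/sham intervention". For the tracheal half: "Following this procedure, a tracheal aspirate will be obtained for detection of α -amylase". If ETT suction is not indicated at the scheduled time, the tracheal specimen may be taken within the next 2 hours. No exception is made for the enrolment pair.

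Human Subjects, section A, applies the same timing to the first pair by name: "Concurrently with delivery of the interventions, paired specimens of oral and tracheal secretions will be obtained at baseline and every 12 hours". Section B repeats the label, saying that specimens "will be obtained at baseline and every 12 hours for up to 14 days". Its list of what is recorded at baseline covers demographics, physiology, ventilator settings, severity and tube details, but no specimen. Table 1 says only that amylase is measured at enrolment and every 12 hours, and gives no order within the session.

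**The concern.** A baseline value should be unaffected by the treatment. This one is collected after allocation is known and during or after the first arm-specific procedure. The NO-ASPIRATE arm has received active oropharyngeal suction, and the usual-care arm a sham without suction.

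The plan intends to test equivalence between groups, to control statistically for differences, and to adjust the amylase models for prognostic covariates. Entry-level microaspiration is a natural candidate for all of these. As scheduled, an arm difference in the enrolment specimen could be chance imbalance or an early effect of the procedure, and the data could not separate the two. Adjusting for it could also remove part of the treatment effect. Aim 3 is worded as exploring change in the tracheal/oral ratio, yet its first observation is not untreated.

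**Working it through.** **1. Order of steps at the first session**

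| Step | Where stated | Relative to first assigned procedure |
|---|---|---|
| Envelope opened | Randomization | before |
| Baseline data (no specimen listed) | Intervention; Human Subjects B | before |
| Oral specimen | Paired specimens; Human Subjects A | during |
| Tracheal specimen | Paired specimens | after, possibly within a further 2 hours |

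Nothing in the documents provides a specimen before the first procedure. Percent positive, mean tracheal value and tracheal/oral ratio all need the tracheal specimen, so none has a pre-treatment value. That the 2-hour allowance applies to the enrolment specimen is an inference from the lack of an exception.

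**2. The plan's own power figure.** The plan states power .87 for H1.1 with a final sample of 400, a 15% reduction and alpha .05. It does not state the two rates; I assume the pilot's 46% and 31%. With 200 per arm, two-sided:
- null SE = √(2 × 0.385 × 0.615 / 200) = 0.04866
- alternative SE = √((0.46 × 0.54 + 0.31 × 0.69) / 200) = 0.04808
- z = (0.15 − 1.96 × 0.04866) / 0.04808 = 1.136, so power = 0.872

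The figure reproduces. No baseline value enters it, so changing the order of collection alters neither the sample size nor the stated power.

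**3. Precision forgone (illustration).** Take one continuous amylase summary per subject, d = 0.25 (the H1.2 effect size), 200 per arm, two-sided 0.05, and an assumed correlation ρ between a clean baseline and the outcome. Power = Φ(0.25 × √(200/2) / √(1 − ρ²) − 1.96).

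| ρ | 0.25 × 10 / √(1 − ρ²) | Power |
|---|---|---|
| 0 | 2.500 | 0.71 |
| 0.3 | 2.621 | 0.75 |
| 0.5 | 2.887 | 0.82 |
| 0.7 | 3.501 | 0.94 |

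The documents give no ρ. The plan's .80 for H1.2 is matched only by a one-sided calculation (0.804). Sidedness is not stated, and the table is two-sided throughout.

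**4. Can the pilot size the early effect?** Positivity was 6/13 = 46% and then 4/13 = 31% one to four hours later, a net change of two subjects. If the same 13 were sampled twice, the smallest possible exact McNemar p arises when two subjects turn negative and none turns positive: 2 × (1/2)² = 0.5. With three against one it is 2 × 5/16 = 0.625. No control group is described. The pilot cannot estimate the shift.

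**5. Why a clean baseline should not be counted as an outcome (illustration).** The plan does not say whether the enrolment specimen enters each subject's percentage. If it did and carried no treatment effect, a subject with four specimens (0, 12, 24 and 36 hours) would show 15 × 3/4 = 11.25 points. Power by the step 2 method would be 0.63.

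**The case against.** The strongest reply is that no stated analysis needs an untreated amylase value. Analysis 1.1 compares percentages between arms; 1.2 and 3.1 model values over time by GEE. None is a change-from-baseline analysis, despite the wording of Aim 3. The formal balance check in Data Analysis covers demographic variables only. Randomisation, stratified by tube type, protects every comparison. This stands.

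Contamination may also be slight. The procedure lasts about 45 seconds and clears the mouth and oropharynx, not the trachea; the sham applies no suction; and about 20 minutes per subject is allotted for procedure and specimens together. A longer gap arises only when ETT suction is not yet indicated, and the documents give no frequency for that. This stands too.

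A reader might infer from the pilot that the enrolment specimen already carries much of the 15-point effect. Step 4 shows why that does not follow. Nor do the documents show that microaspiration at entry is the strongest predictor of later positivity.

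Two neighbouring issues add no weight here because they recur at every specimen: oral collection conditions differ by arm, and a research assistant who knows the arm judges the need for suction.

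Finally, the remedy helps least where the gap is longest, since subjects not yet needing ETT suction would still lack a tracheal baseline. That is a real limit. It does not remove the benefit for the others, and a specimen not taken before treatment cannot be recovered later.

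**Conclusion.** The point holds as a cheap improvement. The pair labelled baseline is post-allocation and is collected during and after the first procedure, so the plan has no pre-treatment amylase value for checking balance, for covariate adjustment, or as the starting point for Aim 3.

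A reader might conclude that the randomised comparison is biased or that Aim 3 cannot be tested. The documents support neither: the between-arm contrasts in 1.1, 1.2 and 3.1 remain valid.

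The loss is precision and interpretability. On the assumptions in step 3, the forgone power for a continuous amylase measure runs from about 0.04 (ρ = 0.3) to 0.23 (ρ = 0.7). The size of any early arm effect on the enrolment specimen is unknown and may be small.

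**What to change.** In the Intervention and paired-specimen sections, Human Subjects section A and Table 1, state that the enrolment oral and tracheal pair is collected by one technique common to both arms, before the envelope is opened and before the first assigned procedure. Leave the need-based ETT suction rule unchanged. If no tracheal specimen is obtainable then, record the tracheal baseline as missing, which is independent of arm because allocation is not yet known. Label any later specimen as post-procedure.

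In Data Analysis, use the pre-treatment value, with a missing-value indicator, in the balance check and as a baseline covariate in the amylase models. State that it is not an outcome.

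The cost is a change of step order at one session, with the same specimens, staff and assays. There are two downsides. Some subjects will lack a tracheal baseline. The common oral technique involves a trade-off: a catheter gives sham subjects one catheter-drawn sample, while another method makes the enrolment oral value less comparable with later trap samples.

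Separately, the Usual Care/Sham section leaves the suction port unoccluded, while the paired-specimen section traps oral secretions during the sham. These passages must be reconciled.

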A prospective, 2-group, single-blind, randomized clinical trial design is planned. The design will allow us to test the impact of the NO-ASPIRATE intervention on outcomes of microaspiration and VAC.

Aims and Hypotheses

Our primary aim is to compare the effects of the NO-ASPIRATE intervention versus usual care on microaspiration in critically-ill intubated patients on MV. Patients often have high volumes of oropharyngeal secretions, and despite existing interventions, microaspiration occurs. Regular removal of secretions that accumulate in the oropharynx is intended to decrease the volume or potential load, and thus reduce microaspiration. Our working hypotheses are that subjects in the NO-ASPIRATE group will have a reduction in microaspiration as measured by the percentage of tracheal specimens that are positive for α -amylase (1.1) and *mean values of α -amylase* (1.2).

A secondary aim is to compare the effects of the NO-ASPIRATE intervention on development of VAC and duration of VAC-free days. By reducing the risk for microaspiration, VAC should be reduced. Our working hypotheses are that the subjects in the NO-ASPIRATE group will have a lower rate of VAC (2.1) and longer duration of VAC-free days (2.2). Another secondary aim is to explore changes in the ratio of α -amylase in the tracheal aspirate versus the mouth over time. Our working hypothesis is that subjects in the NO-ASPIRATE group will have a lower tracheal/oral α -amylase ratio over time (3.1).

Setting and Sample

Setting. The study will be conducted in the ICUs at Orlando Regional Medical Center (ORMC), a division of Orlando Health. ORMC is an 808-bed tertiary care facility that specializes in trauma, emergency care, cardiology, orthopedics, neurosciences, and internal medicine. The hospital serves a 5-county area in Central Florida area with a diverse population of 2.8 million people.¹¹⁹ The ICUs include Trauma (14 beds), Neuroscience (16 beds), Multi-System (10 beds), and Cardiac (10 beds). Nursing and respiratory care practices for airway management are standardized across units. The patients are managed by a team of either

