NO-ASPIRATE Intervention. The NO-ASPIRATE intervention involves enhanced suctioning of the mouth and oropharynx every 4 hours with an oropharyngeal suction catheter. The catheter is 8.25" (21 cm) long (see Figure 2D) and is one that we tested in the simulated setting as being most effective in removing oropharyngeal secretions.⁹⁹ *Figure 5 compares secretion removal with a suction swab (usual care) versus the oropharyngeal suction catheter. This length and pliability of the oropharyngeal suction catheter facilitate manipulation of the catheter around the ETT to reach secretions in the oropharynx. In contrast, suction swabs and tonsil suction devices are shorter and rigid, and do not reach secretions that pool in the oropharynx.*

During the intervention, the oropharyngeal suction catheter will be repositioned to reach both sides of the mouth and the oropharynx. Suctioning will be done using standard suction pressures until secretions are no longer audible or visible, for a duration of about 45 seconds.²⁵ ¹²¹ We have performed this procedure in previous studies without any adverse issues, such as gagging or oral trauma.^{25,93}

However, subject response will be observed and the procedure will be stopped if intolerance is noted.

Usual Care/Sham Intervention. A usual care/sham intervention will be delivered to those in the usual care group. Trained RAs will insert the suction catheter into the subject's mouth and mimic the suction procedure for 45 seconds without occluding the suction port. The usual care/sham intervention will be done every 4 hours.

Data Collection. Data will be collected at enrollment and at regular intervals (Table 1), including demographic and physiological data to describe the sample and *test equivalence between groups*. We will also collect data related to factors that might influence microaspiration and development of VAC to assist in interpretation of findings and be used as possible covariates in statistical analyses. *We anticipate having 4 to 6 subjects enrolled at a time. This estimate was based on consultation with [name] and designed to ensure adequate time to deliver the intervention, enroll new subjects, and record data from the medical record.* Additionally, at this rate of accrual, laboratory will be able to regularly process the α -amylase assays.

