Treatment fidelity and effect of usual care will be addressed by reinforcing existing protocols for head of bed elevation, daily interruption of sedation, and ETT cuff pressure (20-30 cm H₂O). During our every 4 hour rounds, we will monitor and promote adherence, and document potential issues. To control for usual oral care practices, we will deliver oral care suctioning and cleansing/antisepsis interventions to both groups. We will also record documentation of additional oral suctioning interventions and method/tolerance of enteral feedings. Although random assignment of subjects to groups should address potential confounders, we will compare data between groups and control statistically if differences are noted.

Data Management and Integrity. We will record data in electronic format, using spreadsheet or database software, on tablet or laptop computers that are password protected and used solely for the study. Computers will be stored in a locked secured area when not in use. We will use the software data validation features and/or filters for as many variables as possible to ensure accuracy of data entry, including missing data and out-of-range values. These features allow for drop down selection of findings, and specifications of parameters for values that are expected to be recorded. We have successfully used similar procedures in previous studies to ensure consistency and accuracy of data collection. [name] will oversee data management and integrity for the study, and will be assisted by the PD. He has past experience in this role on NIH-funded grants, and is an expert at managing large databases. The PD will monitor study records to ensure completeness. Accuracy of the data collected from the EMR will be reviewed for 10% of subjects during the first month of the study. Errors will be corrected, and re-training will be done as necessary. Following the initial audit, 5% of the files will be audited quarterly for completeness and accuracy; we will create an audit trail to identify and correct issues and/or errors.¹²³ If causes of error other than random variation are identified, we will change our procedures.

Data Analysis

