Subjects will be randomly assigned to each of the two treatment groups at 1:1 ratio. Before analysis, data will be carefully examined for accuracy. Every effort will be made to avoid missing data. Subject characteristics at baseline will be examined to ensure a sound balance on demographic variables between the two groups. For continuous demographic variables, independent two-sample *t* tests will be used to detect differences between the two groups. For categorical demographic variables, the Pearson's chi-square test will be used to examine differences between the two groups. If subject subsets are found to be significantly different for a demographic variable, then this variable will be included into the statistical models. All planned analyses will be based on the intent-to-treat (ITT) population, which consists of all subjects who have been randomized into the NO-ASPIRATE or usual care group. In all analyses, an alpha level of 0.05 will be used.

[figure not shown]

Figure 6. Algorithm for Determining VAC

Aim 1. To compare the effects of the NO-ASPIRATE intervention versus usual care on microaspiration of gastric and oral contents in critically-ill intubated patients. Hypothesis 1.1.

Subjects in the NO-ASPIRATE group will have a significantly lower percentage of tracheal secretions with α -amylase present as compared to those in the usual care group. **Analysis 1.1.** Percentages of tracheal secretions α -amylase present for both groups will be computed. The percentage difference between the two groups will be calculated along with the 95% confidence interval for the percentage difference. The logistic regression including covariates of interest will be used to assess the percentage difference adjusting for the prognostic covariates.

Hypothesis 1.2. Subjects in the NO-ASPIRATE group will have a lower mean value of α -amylase in tracheal secretions as compared to those in the usual care group. **Analysis 1.2.** Values of α -amylase in tracheal secretions will be collected for each subject every 12 hours during study. Treatment effect based on these values over time will be evaluated by the generalized linear models using the generalized estimating equation (GEE) method.^{124,125} In addition, the generalized linear models with prognostic covariates of interest will be used to assess change in mean values of α -amylase over time adjusting for prognostic covariates.

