Confounding Variables. Since we know that oral suctioning and cleansing practices vary widely, we will assume responsibility for oral care interventions for all subjects. This will allow us to truly test the effect of the NO-ASPIRATE intervention versus usual care. Since we will be delivering oral hygiene, we will communicate well with the nursing staff to avoid duplication of procedures. Prior to the study, we will provide information sessions for staff (nurses and RTs) to outline roles of study team members and reinforce existing protocols. We will assess the medical record for additional oral suctioning done by the staff. We will use standard unit supplies for usual care from the oral care kit, and label components to assess if supplies are used by others. Additional suction swabs and catheters are not available to the staff beyond those included in the kit. If the patient needs additional suctioning to manage secretions, the tonsil suction device is readily available. We will promote adherence to existing protocols for head of bed elevation, daily interruption of sedation for weaning assessment, enteral feeding management, and ETT cuff pressure. We will monitor these interventions during rounds, reinforce adherence, and document findings. We will record information related to potential confounders from the EMR. We will compare equivalence between groups and control statistically if indicated. Standard practices to prevent microaspiration could change during the study. We will monitor for potential influences of any new practices, and we will include them in the analyses if warranted. Random assignment of subjects to groups should address potential issues. We will also use the expertise of our consultants.

Biomarker of Microaspiration. Because our focus is on removal of oropharyngeal secretions, we are using α -amylase as a biomarker for microaspiration because it is a specific measure of migration of oral secretions from the oropharynx to the lungs. We considered measuring pepsin; however, it has a short window for detection after aspiration and is specific to gastric contents. Although α -amylase is a newer biomarker for

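### The plan allows adjustment for extra oral suctioning given after randomisation, and does not say whether the adjusted or the unadjusted result decides each hypothesis

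*Combined protocol and SAP*

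**What the plan says.** **Care after randomisation.** The Intervention section and the Figure 4 caption both state: "Additional necessary oral suctioning will be recorded and controlled for, if applicable". Staff give this suctioning between the scheduled procedures, so it follows allocation. Data Collection says that factors which might influence microaspiration and VAC may "be used as possible covariates in statistical analyses". Personnel Training and Fidelity deals with head of bed, cuff pressure, extra suctioning and feeding, and then says "we will compare data between groups and control statistically if differences are noted". Confounding Variables repeats the idea: "We will compare equivalence between groups and control statistically if indicated". Table 1 records extra oral care daily, with testing of group equivalence as its purpose.

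**Baseline variables.** Data Analysis compares demographics by t test or chi-square and adds: "If subject subsets are found to be significantly different for a demographic variable, then this variable will be included into the statistical models".

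**Stratification.** Randomization, and section A of Human Subjects, stratify by ETT type and by nothing else. Table 1 mentions stratifying by tube type as a reason for collecting it. No analysis names it as a model term.

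**Models.** Analyses 1.1 to 3.1 each have a version without covariates (percentage difference, GEE, or Cox with Kaplan-Meier) and a version with unnamed prognostic covariates. The 0.05 level applies to all of them. For 1.2 and 3.1 the wording presents adjustment as an addition. For 1.1, 2.1 and 2.2 there is no such cue.

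**The concern.** Extra suctioning may itself be a result of allocation. Aims and Hypotheses gives the mechanism: "Regular removal of secretions that accumulate in the oropharynx is intended to decrease the volume or potential load, and thus reduce microaspiration". Staff suction extra to manage secretions. If the intervention works as intended, treated patients may need less of it, and the number of extra passes then carries part of the treatment effect. A model that holds this number fixed compares treated and control patients with unlike underlying secretion tendency.

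Bias needs two conditions: the arm changes extra suctioning, and extra suctioning either affects tracheal positivity or shares a cause with it. A rule that calls for control when differences are seen acts most often when the first condition is met.

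Also at stake is which number is the trial's answer. With two results per hypothesis and none named as deciding, the choice can be made after both are known.

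**Working it through.** **1. Reference point.** The plan gives no figure for this issue. Its H1.1 power does reproduce: 46% versus 31% (the pilot rates, inferred as the planning rates), 200 per arm, two-sided 0.05. With pooled proportion 0.385, z = [0.15 − 1.96·√(2·0.385·0.615/200)] / √[(0.46·0.54 + 0.31·0.69)/200] = (0.150 − 0.0954)/0.0481 = 1.136. Power is 0.872, against the stated .87.

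**2. Loss from adjusting for extra suctioning (illustrative).**

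- From the documents: 12-hourly specimens, at least 36 hours and at most 14 days of participation, and a median of 4 days on ventilation.
- Assumed: the arm (T) lowers load by 0.5 SD; usual-care positivity is 47%; log-SD of stay is 0.9; extra suctioning has base rate b per day and rises with load at log-slope k.
- Loads: S1 = −0.5T + e1 drives suctioning and S2 = −0.5T + e2 drives positivity, with corr(e1, e2) = ρ.
- Outcome: logit P(positive) = −0.16 + 1.3·S2. Suctions ~ Poisson(days·b·exp(k·S1)).
- Regress each subject's percentage positive on arm, with and without log(1 + suctions/day). Loss = 1 − adjusted/unadjusted. The unadjusted difference is about 12 points.

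Shared load (ρ = 1):

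| b per day | k = 0.3 | k = 0.7 | k = 0.3, unrelated variation added | k = 0.7, unrelated variation added |
|---|---|---|---|---|
| 0.25 | 7% | 29% | 4% | 17% |
| 1 | 22% (11.8 to 9.2 points) | 58% (11.8 to 4.9) | 6% | 25% |
| 3 | 42% | 78% | 8% | 29% |

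Unrelated variation is an N(0,1) term added to the log suction rate. At b = 1 and ρ = 0.5 the losses are 11% and 29%, or 3% and 13% with unrelated variation. At ρ = 0 they are 0 to 1%. At k = 0 they are 0%. A logistic model with one outcome per subject (b = 1, ρ = 1) loses 8% and 32%.

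**3. How often the trigger acts.** The plan does not define a difference. Taking p < 0.05 with 200 per arm and b = 1, the arms differ in extra suctioning in 6%, 64% and 95% of trials for k = 0, 0.3 and 0.7. With unrelated variation the figures are 5%, 18% and 50%.

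**4. Direction.** Take a linear case with no true effect, where a latent burden drives suctioning (0.6, residual SD 0.8) and outcome (0.5). If the arm lowers suctioning by a SD, the adjusted estimate is off by a·(0.6·0.5)/(0.6² + 0.8²) = 0.3a. For a = 0.25, 0.5 and 1 this is 0.075, 0.15 and 0.30 SD, against the intervention. Simulation gave 0.07, 0.15 and 0.30.

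**5. Choosing between two results.** Under the null, with 5 to 10 baseline covariates explaining 10% to 30% of variance, accepting whichever result is significant gives a rejection rate of 0.070 to 0.075, against about 0.05 for either alone.

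**6. ETT type left out.** With 65% SS-ETT, positivity gap g and overall rate p, the variance share is r = 0.65·0.35·g²/[p(1 − p)], and true alpha = 2·[1 − Φ(1.96/√(1 − r))]. For assumed gaps of 0, 11, 17 and 31 points, r = 0, 0.011, 0.026 and 0.088, and alpha = 0.050, 0.049, 0.047 and 0.040. Power with ETT type in the model moves from 0.866 to 0.867 (no gap), 0.871 to 0.877 (15 points) and 0.885 to 0.907 (30 points). The demographic rule would not bring ETT type in: under stratified blocks of assumed sizes 4 and 6, its balance test was significant in 0 of 500 runs per scenario.

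**7. Demographic tests.** The chance that at least one variable enters by luck is 1 − 0.95⁴ = 19% for four independent variables, and 1 − 0.95⁹ = 37% with five comorbidities added. The counts are a choice, since Table 1's demographic block lists more. Test-then-adjust gave a type I error of 0.041 to 0.044, so there is no inflation.

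**The case against.** The permission is conditional. The Analysis paragraphs name no care variable, and every hypothesis keeps a version without covariates. The design also limits any arm difference in extra suctioning: research staff swab-suction both arms every 4 hours, unit staff are blinded, and the study team takes over oral care. The protocol says that swabs and tonsil devices "do not reach secretions that pool in the oropharynx", which argues against a strong direct effect of extra suctioning on the outcome. All of this stands and favours the low rows of the table. It does not exclude a common cause through secretion load, and it does not say which result decides.

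Some stronger readings are tempting but not supported:

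- *The primary result will be adjusted for a mediator.* The text permits this and does not require it.
- *Adjustment would create a false benefit.* Under the plan's own mechanism it shrinks the effect.
- *Head of bed, cuff pressure and feeding raise the same problem.* The documents give no route by which the arm would change them. If it does not, differences arise by chance and adjustment does little harm.
- *Leaving out ETT type, or testing demographics, biases the effect.* Neither does.

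**Conclusion.** The concern stands as a gap in specification that should be closed. Adjusting for extra suctioning can remove part of a real effect, and the difference-based trigger acts most often when it can. How much is lost cannot be known from the documents. It ranges from nothing to most of the effect, depending on an assumed suction rate, on how steeply suctioning follows load, and on how far that load is shared with microaspiration. No single percentage from the table should be read as an estimate.

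The lack of a deciding result matters alongside this, because it is what would let an attenuated or a favourable version become the headline. Its cost under the null is modest, and it holds only if the choice is made after seeing both. ETT type and the demographic rule are minor: the first makes the test slightly conservative, and the second lets chance pick the model.

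**What to change.** Amend the SAP wording as follows. The data are already collected.

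(a) For each Aim 1 and Aim 2 hypothesis, name as deciding the arm comparison adjusted for ETT type only: the percentage difference with 95% CI for H1.1 and H2.1, the GEE for H1.2 and the Cox model for H2.2. The unadjusted result is supporting. Use the same GEE form for the exploratory Aim 3.

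(b) In the Intervention section and the Figure 4 caption, replace the control clause. In Personnel Training and Fidelity and in Confounding Variables, replace the difference-triggered rules as far as they concern subject-level care after randomisation. Suggested text: *reported by arm, and used only in a labelled sensitivity analysis*.

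(c) Delete the significance-based entry rule in Data Analysis. Any further baseline adjustment (for example age, diagnoses and comorbidities from Table 1) is a supporting analysis, with covariates fixed before unblinding.

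(d) Keep the allowance for site-wide change, "We will monitor for potential influences of any new practices, and we will include them in the analyses if warranted", as a sensitivity analysis.

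The cost is that the deciding result is not adjusted for chance imbalance in other baseline variables. The supporting analysis in (c) covers that.
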